7. RATIONALE AND BACKGROUND

MM is a hematological malignancy originating in plasma cells in the bone marrow.^{1,2} Healthy plasma cells secrete antibodies, also known as immunoglobulins, to fight infection and act as the humoral line of defense.^{1,2} Plasma cells that have become cancerous (ie, myeloma cells) proliferate and displace normal cell production in bone marrow, among other effects on the immune system. As a consequence, the general production of antibodies is impaired, decreasing the body's supply of antibodies.³ MM is characterized by an increase in non-functional monoclonal proteins (M proteins), a decrease in blood count, renal failure, end-organ damage, susceptibility to infections, and bone weakness.¹⁻³ The incidence of MM was 7.4 per 100,000 people in the US from 2016-2020, while the 5-year relative survival from 2013 to 2019 was 59%.⁴ MM is the second most prevalent hematological malignancy and accounted for approximately 1.8% of all new cancer cases in 2023.^{5,6}

Many therapies for MM exist, and clinical advances continue to change the treatment landscape. The advent of therapies, such as proteasome inhibitors (PIs), IMiDs, and mAbs, has increased the OS of MM patients.⁷⁻⁹ Despite numerous advances in the available therapies for MM, most patients with MM will either relapse (fail to respond to treatment) or become refractory (have their treatment fail).¹⁰ These patients are collectively referred to as having RRMM. Given relapse to later lines confers progressively worse outcomes including shorter survival time, there is a need to investigate alternative treatment options in this setting.^{9,10}

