9.2. Setting

This study will evaluate adult patients with RRMM who initiate elranatamab. Patients will enter (i.e., index) on the first observed elranatamab claim between 14 August 2023 and the end of data (defined as the latest data at the time of the specified analysis). Limited eligibility criteria will be applied.

Study Period: Start of data availability (01 January 2016) to the end of data

MM diagnosis window: Start of data availability (01 January 2016) to index date

Index date: First elranatamab claim after initial MM diagnosis

Observability: At least 180 days of continuous closed-claims medical and pharmacy enrollment prior to index (inclusive)

[figure not shown]
Baseline period for MM-related treatments and MM-related comorbidities: MM diagnosis to one day prior to index date (unless otherwise specified)

CCI and baseline HCRU assessment window: 180 days prior to index date to index date.

Follow-up: Index date until death, the earliest of the end of data, or end of continuous enrollment (unless otherwise noted). Alternative censoring criteria will be applied for certain outcomes (such as OS, TTD, and TTNT/D); see [Section 9.7](#) for more details.

Figure 1 reflects the time periods of interest in the study cohort.

Figure 1. Study Schematic for Patients Receiving Elranatamab

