9.3. Variables

Table 1 includes definitions and assessment periods for all study variables that will be used as eligibility criteria. The full code list can be found in ANNEX 2. ADDITIONAL INFORMATION.

Table 1. Variables Used to Determine Eligibility

Variable	Operational Definition	Role	Assessment Period
Elranatamab	Prescription claim or medical claim with a National Drug Code (NDC), Healthcare Common Procedure Coding System (HCPCS), ICD-10 code or generic name in the IP, non-IP or pharmacy setting for elranatamab	Inclusion	Index event
Teclistamab	Prescription claim or medical claim with an NDC, HCPCS, ICD-10 code or generic name in the IP, non-IP or pharmacy setting for teclistamab	Exclusion	All available data to index date

Variable	Operational Definition	Role	Assessment Period
Age	Age is greater than or equal to 18 years and is not missing	Inclusion	Index date
MM diagnosis	Medical claim in the IP or non-IP setting with an ICD-10 code for MM	Inclusion	All available data to index date
Observability	Closed-claims medical and pharmacy enrollment	Inclusion	180 days prior to index date to index date (inclusive)

Table 2 includes definitions and assessment periods for all study variables that will be used as baseline and treatment characteristics. The full code list can be found in ANNEX 2.
 ADDITIONAL INFORMATION. If applicable, the frequency and percentage of patients with missing data for each variable will be described.

Table 2. Variables Used to Determine Baseline and Treatment Characteristics

Objective	Variable	Definition	Assessment Period(s)
1	Age	Age in years (continuous)	Index date
1	Sex	Categorical sex Male Female	Index date
1	Race/Ethnicity	Categorical race and ethnicity Caucasian African American Asian or Pacific Islander Hispanic or Latino Other	Start of data availability to index date

Objective	Variable	Definition	Assessment Period(s)
		Unknown	
1	Region	Categorical region, assessed as the most recent value from index date Northeast Midwest West South	Start of data to index date
	Insurance type	Categorical insurance type, assessed as the most recent value to index date Commercial Medicaid Medicare Other Unknown	180 days prior to index date to index date
1	Location (Zip code)	Categorical zip code assessed as the most recent value from index date. The full categories will be reported during implementation.	Index date
1	Care setting	Categorical care setting for elranatamab or teclistamab administration IP Non-IP Pharmacy	Index date

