1	Antifungal Medication ¹	Medical claim with an NDC, HCPCS, generic name or CPT code in the IP, non-IP, or pharmacy setting for antifungal medications (dichotomous)	14 days prior to index date to 1 day prior to index date Index date to the end of follow-up
1	Intravenous immunoglobulin ¹	Medical claim with an NDC, HCPCS, generic name, CPT, or ICD-10 procedure code in the IP, non-IP, or pharmacy setting for intravenous	14 days prior index date to 1 day prior to index date

Objective	Variable	Definition	Assessment Period(s)
		immunoglobulin administration (dichotomous)	Index date to the end of follow-up
1	Other hematological malignancies	Medical claim with an ICD-10 code in the IP or non-IP setting for hematological malignancies other than MM (dichotomous)	MM diagnosis to 1 day prior to index date
1	Any non-hematological malignancy	Medical claim with an ICD-10 code in the IP or non-IP setting for non-hematological malignancies (dichotomous)	MM diagnosis to 1 day prior to index date
1	Plasma cell leukemia	Medical claim with an ICD-10 code in the IP or non-IP setting for plasma cell leukemia (dichotomous)	MM diagnosis to 1 day prior to index date
1	Bone lesions	Medical claim with an ICD-10 code in the IP or non-IP setting for bone lesions (dichotomous)	MM diagnosis to 1 day prior to index date
1	Peripheral neuropathy	Medical claim with an ICD-10 code in the IP or non-IP setting for peripheral neuropathy (dichotomous)	MM diagnosis to 1 day prior to index date
1	Any infection	Medical claim with an ICD-10 code in the IP or non-IP setting for any infection of the following types (dichotomous): COVID-19 Sinusitis Bronchitis Adenoviral pneumonia Cytomegaloviral pneumonitis Other Pneumonia Upper respiratory tract infection	MM diagnosis to 1 day prior to index date

Objective	Variable	Definition	Assessment Period(s)
		
Sepsis
 
Cytomegaloviral infection
 
Pneumocystis jiroveci pneumonia (PJP)
 
Hepatitis C
 
Hepatitis B
 
Other infectious hepatitis
 
Helicobacter pylori
 
Candida esophagitis
 
Urinary tract infection
	
1	Use of intravenous anti-infective	Medical claim with an NDC code generic name, CPT, or HCPCS code in the IP, non-IP, or pharmacy setting for anti-infective where the route of administration is intravenous for an intravenous anti-infective (dichotomous)	MM diagnosis to 1 day prior to index date

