Intravenous immunoglobulin	Baseline characteristic - Treatments, Dexamethasone	Claims data	
HCPCS (Mapped via Athena – OHDSI using brand name): J1556, C9130, J1557, J1559, C9270, Q4097, Q4092, Q4091, Q4088, Q4087, J1572, J1569, J1568, J1562, J1459, J1576, J1555, C9072, J1551, J1554, J1558
 
Brand Name (mapped to NDC codes via First Data Bank): Asceniv, Bivigam, Gammagplex, Privigen, Octagam, Flebogamma/Flebogamma Dif, Panzyga, Gammagard Liquid, Flebogamma, Gamunex, Gammagard N, LAndoglobulin, Polygam S/D, Gammagard S-D, Gammagard S/D, Gammagard,
	
Mayo Clinic (2024) Athena – OHDSI

			Panglobulin, Carimune, Carimune Nf Nanofiltered, Venoglobulin-S, Iveegam En, Flebogamma Dif	
Other hematological malignancies	Baseline characteristic - Clinical	Claims data	ICD-10 Diagnosis: Lymphoma; malignant plasma cell neoplasm; leukemia; other and unspecified malignant neoplasms of lymphoid, hematopoietic, and related tissue; and myelodysplastic syndrome: C81-C96, D46 (Excluding C90.0x)	Maziarz et al. (2024)
Any non-hematological malignancy	Baseline characteristic - Clinical	Claims data	ICD-10 Diagnosis: C0x.x, C1x.x, C2x.x, C30.x, C31.x, C32.x, C33.x, C34.x, C37.x, C38.x, C39.x, C40.x, C41.x, C43.x, C45.x, C46.x, C47.x, C48.x, C49.x, C50, C51-C58.x, C60-63.x, C76.x, C80.1	Glasheen et al. (2019)
Plasma cell leukemia	Baseline characteristic - Clinical	Claims data	ICD-10 Diagnosis: C90.1x	Wu et al. (2017)
Graft vs host disease	Baseline characteristic - Clinical	Claims data	ICD-10 Diagnosis: D89.81x	Huang et al. (2023)
Benign bone lesions	Baseline characteristic - Clinical	Claims data	ICD-10 Diagnosis: D16.0-D16.9, M85.0, M85.4-M85.6, D48.0	Muran et al. (2023)
Peripheral neuropathy	Baseline characteristic - Clinical, AE	Claims data	ICD-10 Diagnosis: G90.50, G90.513, G90.511, G90.512, G90.519, G90.521, G90.529, G90.522, G90.523, G90.59, G54.0, G55, G54.2, G54.4, E08.41, E09.41, E10.41, E11.41, E13.41, G57.70, G57.71, G57.72, G57.73, G59, G57.80, G57.81, G57.82, G57.83, G58.8, G58.9, G64, G61.0, M05.50, M05.511, M05.512, M05.519, M05.521, M05.522, M05.529, M05.531, M05.532, M05.539, M05.541, M05.542, M05.549, M05.551, M05.552, M05.559, M05.561, M05.562, M05.569, M05.571, M05.572, M05.579, M05.59, E08.40, E08.42, E09.40, E09.42, E10.40, E10.42, E11.40, E11.42, E13.40, E13.42, G13.0, G13.1, A36.83, A52.15, G63, M34.83, G62.1, G61.1, G62.0, G62.2, G62.82, G61.81, G62.81, G61.89,	Song et al. (2019)

PFIZER CONFIDENTIAL

Redacted

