Diabetes with chronic complications	Baseline characteristic - Clinical	Claims data	ICD-10 Diagnosis: E08.2x, E08.3x, E08.4x, E08.5x, E09.2x, E09.3x, E09.4x, E09.5x, E10.2x, E10.3x, E10.4x, E10.5x, E11.2x, E11.3x, E11.4x, E11.5x, E13.2x, E13.3x, E13.4x, E13.5x	Glasheen et al. (2019)

PFIZER CONFIDENTIAL

Redacted

Mild or moderate renal disease	Baseline characteristic - Clinical	Claims data	ICD-10 Diagnosis: I12.9, I13.0, I13.10, N03.x, N05.x, N18.1, N18.2, N18.3, N18.4, N18.9, Z94.0	Glasheen et al. (2019)
Severe renal disease	Baseline characteristic - Clinical	Claims data	ICD-10 Diagnosis: I12.0, I13.11, I13.2, N18.5, N18.6, N19.x, N25.0, Z49.x, Z99.2	Glasheen et al. (2019)
Hemiplegia or paraplegia	Baseline characteristic - Clinical	Claims data	ICD-10 Diagnosis: G04.1, G11.4, G80.0, G80.1, G80.2, G81.x, G82.x, G83.x	Glasheen et al. (2019)
Human immunodeficiency virus	Baseline characteristic - Clinical	Claims data	ICD-10 Diagnosis: B20.x	Glasheen et al. (2019)
Metastatic solid tumor	Baseline characteristic - Clinical	Claims data	ICD-10 Diagnosis: C77.x, C78.x, C79.x, C80.0, C80.2	Glasheen et al. (2019)
Any malignancy	Baseline characteristic - Clinical	Claims data	ICD-10 Diagnosis: C0x.x, C1x.x, C2x.x, C30.x, C31.x, C32.x, C33.x, C34.x, C37.x, C38.x, C39.x, C40.x, C41.x, C43.x, C45.x, C46.x, C47.x, C48.x, C47.x, C48.x, C49.x, C50.x, C51-C58.x, C60-C63.x, C76.x, C80.1, C81.x, C82.x, C83.x, C84.x, C85.x, C88.x, C9x.x	Glasheen et al. (2019)
Albumin serum	Baseline characteristic - Lab	Claims data	An event in the lab results table where the result_abbrev is albumin serum and result_units are g per dL	
ALT	Baseline characteristic - Lab	Claims data	An event in the lab results table where the result_abbrev is ALT and result_units are IU per L	
AST	Baseline characteristic - Lab	Claims data	An event in the lab results table where the result_abbrev is AST and result_units are IU per L	
Neutrophil count	Baseline characteristic - Lab	Claims data	An event in the lab results table where the result_abbrev is neutrophils count and result_units are thousand per μ L	

PFIZER CONFIDENTIAL

Redacted

Creatinine	Baseline characteristic - Lab	Claims data	An event in the lab results table where the result_abbrev is creatinine serum and result_units are mg per dL	
Hemoglobin	Baseline characteristic - Lab	Claims data	An event in the lab results table where the result_abbrev is hemoglobin and result_units are g per dL	

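### Table 2 defines a baseline variable as bone lesions of any kind, but the only code list for it in Annex 2 is headed as benign bone lesions; name and codes must be aligned.

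*Protocol*

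**What the plan says.** Section 9.3, Table 2 defines the Objective 1 baseline variable Bone lesions as "Medical claim with an ICD-10 code in the IP or non-IP setting for bone lesions (dichotomous". Nothing in the definition limits it to benign lesions. The assessment window runs from MM diagnosis to the day before index. For codes, the same section states: "The full code list can be found in ANNEX 2".

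Annex 2 has no row named Bone lesions. Its one bone-lesion row is headed "Benign bone lesions", has the role of a clinical baseline characteristic, and gives "ICD-10 Diagnosis: D16.0-D16.9, M85.0, M85.4-M85.6, D48.0".

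Two other places bear on what was meant. Section 9.2 sets "Baseline period for MM-related treatments and MM-related comorbidities: MM diagnosis to one day prior to index date", which is the window that Table 2 gives this variable. Section 7 includes "renal failure, end-organ damage, susceptibility to infections, and bone weakness" among the features of the disease.

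**The concern.** A variable with a broad name rests on a list with a narrower heading. In a cohort selected for multiple myeloma, a reader who sees a row called Bone lesions will naturally take it to include myeloma bone disease. If the list behind it is the benign one, the printed percentage answers a different question, and nothing in the table would reveal that.

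The variable belongs to Objective 1, which is a primary objective, and Exploratory Objective 3 replicates it in the teclistamab cohort. At stake is the correctness of one descriptive row per cohort in each remaining refresh and in the final report.

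The mismatch is unlikely to correct itself. Section 9.8 says that variables will be coded from the codes in the protocol and that the protocol will be strictly followed. A second analyst who checks the programming against the protocol would confirm the benign list. The limitations in Section 9.9 cover coding error in general but do not say that this variable is confined to benign codes.

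**Working it through.** There is no planned figure to reproduce, so the check compares the texts and then asks what the reported percentage would measure.

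**1. Is the benign row the counterpart of the Table 2 variable?** The order of rows says so.
- Table 2: other hematological malignancies, non-hematological malignancy, plasma cell leukemia, *bone lesions*, peripheral neuropathy, any infection.
- Annex 2: other hematological malignancies, non-hematological malignancy, plasma cell leukemia, graft versus host disease, *benign bone lesions*, peripheral neuropathy, any infection.

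Apart from the extra graft versus host row, the sequence is the same, and the benign row stands where the bone-lesion row should be.

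**2. Could another annex row supply the missing codes?** None does.
- The row with "ICD-10 Diagnosis: C77.x, C78.x, C79.x, C80.0, C80.2" belongs to the metastatic solid tumor component of the Charlson index and is not linked to Bone lesions.
- C40.x and C41.x appear only in the two malignancy rows (non-hematological malignancy, and the Charlson any-malignancy component).
- No row is headed for osteolysis, pathological fracture or myeloma bone involvement.

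**3. Is this superseded text?** No. The amendment log in Section 5 records that version 2.0 updated the annex and changed the malignancy component of the Charlson index. It does not mention this variable, so both the Table 2 row and the annex row are current.

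**4. What would be reported?** Let N be the cohort size, B the set of patients with at least one listed code in the window, and M the set with myeloma bone disease. The reported figure is

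reported % = 100 × |B| / N.

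- If any bone lesion is intended, the target is 100 × |M ∪ B| / N. The shortfall is 100 × |M not in B| / N, which is zero or positive, so the figure can only be too low or equal.
- If myeloma bone disease alone is intended, the target is 100 × |M| / N. The error (reported minus target) is 100 × (|B not in M| − |M not in B|) / N. Patients are misclassified in both directions, and the sign of the net error is not fixed by the code list.
- If benign lesions are intended, the number matches its list and only the label is wrong.

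The protocol gives neither |M| nor |B|, nor their overlap, so no size follows in the first two cases.

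**5. Where is the variable used?** It is not an eligibility variable (Sections 9.2.1 and 9.2.2, Table 1), not an outcome (Table 3), and not the basis of the one baseline subgroup named in Section 9.7.1, which is availability of a laboratory observation.

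**The case against.** The strongest reply is that intent is inferred, and this stands. The protocol never says that Bone lesions means myeloma bone disease. The window does not settle it, because hypertension and non-hematological malignancy share it. Hypercalcemia, renal failure and extramedullary disease come several rows later in Table 2 and are not neighbours of this row. The phrase "susceptibility to infections, and bone weakness" is disease background, not a variable definition.

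It can also be said that Annex 2 does not map one-to-one to the tables. Graft versus host disease has an annex row but no Table 2 variable, and Renal failure in Table 2 has no annex row of that name. So the word benign may have been dropped from Table 2, the list may be the wrong one, or the right list may have been left out. The matching row order makes the third reading less likely but does not choose between the first two. All three leave a defect in the current text; they differ in the remedy.

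A reader might infer more than the documents support:
- *That the variable has almost no sensitivity for myeloma bone disease, or that the printed percentage will be far too low.* The protocol gives no prevalence and no information on how often myeloma lesions are billed under the listed codes. It also prints no descriptors for the codes, so that they are benign rests on the row heading. In general ICD-10 nomenclature, D48.0 denotes uncertain behavior, so the list may not be purely benign.
- *That a comparison of elranatamab with teclistamab would be spoiled.* Section 9.7 plans no formal comparison and reports each cohort separately, so harm is limited to informal side-by-side reading.
- *That the published table will certainly carry the broad name.* The table shells are a standalone document listed in Annex 1 and are not available here.

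**Conclusion.** The inconsistency is real and should be corrected. Table 2 names and defines the variable without restriction, while the only list behind it is headed as benign and has no counterpart elsewhere in the annex for myeloma-related bone disease. Applied as written, the Bone lesions row would count only the listed codes and would miss patients whose only bone disease is myelomatous, unless they also carry one of those codes.

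The conclusion assumes that analysts follow the protocol's code list, as Section 9.8 says they will, and that the reported row keeps its Table 2 name. It does not depend on deciding which concept was intended: if the benign list is right, the label is wrong; if the label is right, the list is wrong.

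The consequence is one misdescribed baseline characteristic per cohort, of unknown numerical size. No result on administration, resource use, safety or effectiveness depends on it.

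**What to change.** State which concept is intended and make Table 2, Annex 2 and the table shells agree.

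- **If myeloma bone disease is intended:** replace the annex list with codes for malignant or myeloma bone involvement, confirmed by the coding lead, and name the variable accordingly in both places.
- **If the benign list is intended:** rename the Table 2 variable and the reported row as benign bone lesions, so that it is not read as a feature of myeloma.

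If results already delivered used the benign list under the broader name, the final report should say so.

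The cost is one code-list or label change and, where codes change, a rerun of one descriptive row per cohort. Claims codes for myeloma bone disease may be incompletely recorded, so the corrected percentage should be presented with that caveat. The timetable in Section 6 allows the change: version 2.0 is dated 31 July 2025, and refresh 3 (9 September 2025), refresh 4 (20 December 2025) and the final report (28 February 2026) all follow it.

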9.5. Study Size

This retrospective cohort study will be largely descriptive in nature; sample size calculations are not directly applicable. At the time of the study, the dataset included over 700,000 patients with a claim for MM and 56 patients with a claim for elranatamab. The results of this study will be updated on a quarterly basis becomes available.

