9.7.1. Descriptive Analysis

Dichotomous and categorical variables will be summarized by the number and percentage of patients in each category. Continuous variables will be described using mean (SD), median (IQR), minimum, and maximum. If applicable, the frequency and percentage of patients with missing data for each variable will be described. Furthermore, baseline characteristics will be assessed among elranatamab or teclistamab patients with and without a laboratory observation.

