9.8. Quality Control

Redacted will code measures for cohort identification, outcomes, and other variables of interest based on codes and algorithms described in this protocol. This protocol will be strictly followed when conducting the analysis of this study. All cohorts developed, statistical

analyses implemented, and tables completed will undergo quality control review by at least one additional analyst or scientist under the supervision of the Study Lead. The Study Lead will review all results tables and other final deliverables to confirm accuracy, logical flow, and appropriate format.

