			G62.89, G61.9, G62.9, H46.3, M54.10, M54.18, M79.2, R20.0, R20.1, R20.2, R20.3, R20.8, R20.9	
Any infection	Baseline characteristic - Clinical	Claims data	An ICD-10 Diagnosis Code for any of the following types of infections. See the rows below for codes for each infection type. COVID-19, Adenoviral pneumonia, Cytomegaloviral pneumonitis, Other Pneumonia, Upper respiratory tract infection, Sepsis, Cytomegaloviral infection, PJP, Hepatitis C, Hepatitis B, Other infectious hepatitis, Helicobacter pylori, Candida esophagitis, Urinary tract infection	N/A
Use of intravenous anti-infective	Baseline characteristic - Clinical	Claims data	See “Antivirals,” “Antibiotics,” and “Antifungals” and where service category = injection/infusion drugs or where route = injectable or route array has injectable in it OR HCPCS/CPT codes that indicate IV administration of an anti-infective	N/A
Absolute neutrophil count (for Neutropenia)	Baseline characteristic - Clinical, AE	Claims data	White blood cell count x the percentage of neutrophils White blood cell count: Results_value in the lab results table where the result_abbrev is wbc and result_units are thousand per μ L Percent Neutrophil: Results_value in the lab results table where the result_abbrev is neutrophils percent and result_units are percent White blood cell count and percent neutrophil results must occur on the same day	Severe Chronic Neutropenia International Registry
Neutropenia	Baseline characteristic - Clinical, AE	Claims data	ICD-10 Diagnosis: D70.x or Absolute neutrophil count < 1500 cells per μ L	Kim et al. (2022) Lustberg et al. (2012)

PFIZER CONFIDENTIAL

Redacted

Hypercalcemia	Baseline characteristic - Clinical	Claims data	ICD-10 Diagnosis: E83.52 or value in the GDD table where test is hypercalcemia and result_units are mg/dL and result_value is > 11.5	Kumi et al. (2024) CTCAE v6 (2020)
Hepatotoxicity	Baseline characteristic - Clinical, AE	Claims data	ICD-10 Diagnosis: K71.x	Banerjee et al. (2023)
Amyloidosis	Baseline characteristic - Clinical	Claims data	ICD-10 Diagnosis: E85.4x, E85.8x, E85.9x	Quock et al. (2018)
Hypertension	Baseline characteristic - Clinical	Claims data	ICD-10 Diagnosis: I10x-I15x	Angier et al. (2019)
Extramedullary plasmacytoma	Baseline characteristic - Clinical	Claims data	ICD-10 Diagnosis: C90.2x	Ellington et al. (2021)
CCI score	Baseline characteristic - Clinical	Claims data	See components below	Glasheen et al. (2019)

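### Use of intravenous anti-infective is defined by intravenous route in Table 2 but by any injectable route in Annex 2, so non-intravenous injections can be counted under an intravenous label

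*Protocol*

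**What the plan says.** Section 9.3, Table 2, lists 'Use of intravenous anti-infective' as a yes/no baseline characteristic under Objective 1, assessed from MM diagnosis to the day before index. It asks for a claim for an "anti-infective where the route of administration is intravenous for an intravenous anti-infective (dichotomous").

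Annex 2 has a row with the same variable name. It refers to its antiviral, antibiotic and antifungal lists and accepts those products "where service category = injection/infusion drugs or where route = injectable or route array has injectable in it". It then adds "OR HCPCS/CPT codes that indicate IV administration of an anti-infective".

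Three other passages show how the two definitions are meant to work together:

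- Section 9.3 says of the Table 2 variables that "The full code list can be found in ANNEX 2".
- Section 9.8 says that measures will be coded "based on codes and algorithms described in this protocol", and that the protocol will be followed strictly.
- Section 9.7.1 fixes the reporting: "Dichotomous and categorical variables will be summarized by the number and percentage of patients in each category".

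**The concern.** The name and the Table 2 definition promise intravenous treatment. The annex algorithm delivers something broader, because an injection need not be intravenous. An intramuscular or subcutaneous claim fails the Table 2 definition but can pass the annex rule.

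Both passages are current text, and Section 9.8 tells the programmer and the quality control reviewer to follow the protocol strictly. Two analysts who do so can build two different variables, and nothing in the protocol says which definition prevails. If the annex is followed, as its role as code list suggests, the results table will show a percentage under an intravenous label that may include patients who had only non-intravenous injections.

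What is at stake is the meaning of one descriptive percentage. It falls under a primary objective, and Exploratory Objective 3 repeats it in the teclistamab cohort. The window can be long: MM diagnosis may date back to the start of data on 01 January 2016, and a single qualifying claim is enough to count a patient.

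**Working it through.** The plan states no figure to reproduce. The check compares the two definitions and works through the Boolean logic.

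**Inputs**

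| Element | Table 2 (Section 9.3) | Annex 2 |
|---|---|---|
| Product | an anti-infective | a product in the antiviral, antibiotic or antifungal lists |
| Route condition | intravenous | injection/infusion service category, or injectable route, or injectable among the listed routes |
| IV-specific codes | code types named, subject to the route condition | a separate alternative joined by OR |

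**Step 1: the annex rule as logic.** Let A be a listed anti-infective, S the injection/infusion service category, R an injectable route, M a route array that contains injectable, and V a code that indicates intravenous administration of an anti-infective. The natural reading is

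(A and (S or R or M)) or V.

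**Step 2: does any clause require intravenous route?** S, R and M do not. V does, but it is joined by OR. A claim that satisfies A and R is counted whether or not V holds, so V can add claims and cannot remove any.

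**Step 3: a test case.** Take a claim for a listed antibiotic given as a non-intravenous injection, with route recorded as injectable.

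- Table 2: the route is not intravenous, so the patient is not counted.
- Annex 2: A and R both hold, so the patient is counted.

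**Step 4: direction.** Take injectable to include intravenous, as the annex appears to intend. Let p be the share of patients with a true intravenous claim that the rule captures, and q the share of the remaining patients whose only qualifying claims are non-intravenous injections. Then

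reported share = p + (1 − p) × q, and excess = (1 − p) × q ≥ 0.

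The excess is zero only if q = 0 or p = 1. The documents give neither p nor q, so no value can be put on it.

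**Step 5: precedence.** The annex text has no brackets. Read with AND binding before OR, it becomes (A and S) or R or M or V, which would admit injectable products that are not anti-infectives at all. That is clearly not intended, but the text does not rule it out.

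**Step 6: reach.** Annex 2 gives the variable only a baseline role. It is not among the eligibility variables in Table 1 or the outcomes in Table 3, and the methods for TTD, adverse events, OS and TTNT/D (Sections 9.7.4, 9.7.6 and 9.7.7) do not use it.

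**The case against.** The strongest reply is that Annex 2 translates clinical concepts into the fields that the data vendor supplies, as it also does for laboratory results and for inpatient, outpatient and emergency visits. Injectable may be the closest available route value, and the annex rule may be a deliberate proxy. That is plausible, and it means that a restriction to intravenous route may not be feasible. But the protocol does not say so. Table 2 still says intravenous, and the limitations in Section 9.9 warn of coding error in general without mentioning route. The proxy reading changes which remedy applies; it does not remove the mismatch.

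Several stronger conclusions are tempting, and the documents do not support them:

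- **A biased measure of serious prior infection.** A reader might take intravenous treatment as a marker of severity. The protocol gives the variable no such role, and prior infection has its own Table 2 row based on diagnosis codes.
- **Named drugs as proof.** A reader might point to agents in the annex lists that are given by other injection routes. Apart from the intravenous immunoglobulin row, the annex lists carry no routes of administration, so such examples rest on outside knowledge. The logical point does not need them.
- **Products with several possible routes counted however given.** This assumes that the route array describes the product and not the claim. The protocol does not define the field.
- **A shift measured in standard errors at 56 patients.** The 56 in Section 9.5 are patients with an elranatamab claim, counted before the eligibility criteria and the planned refreshes. They are not the analysis cohort, and any assumed rate of misclassification would be invented.

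It is also fair to say that the consequence is small: Section 9.7 plans no formal comparison between groups.

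**Conclusion.** The point stands as a contradiction between definition and algorithm. Table 2 requires intravenous route; Annex 2 accepts injectable route or an injection/infusion category and does not require intravenous use. If the annex is programmed as written, the Objective 1 percentage can only be overstated relative to its label.

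This rests on two assumptions: that the annex and not Table 2 is what gets programmed, and that injectable covers intravenous in the data. Whether any patient is in fact misclassified depends on field values that the documents do not show, so the size is unknown and could be nil. Eligibility, adverse event outcomes, TTD, OS and TTNT/D are unaffected. The correction is worth making because it is cheap, but it is minor.

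**What to change.** Make the Table 2 definition and the Annex 2 algorithm agree, and bracket the annex rule so that the product condition clearly applies to every route and service-category clause. Which change to make depends on what the route field holds:

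- **If the data carry an intravenous route value:** restrict Annex 2 to that value, plus HCPCS/CPT codes that denote intravenous administration, and drop the injectable and injection/infusion clauses.
- **If the data hold only injectable:** keep the annex rule, rename the variable 'injectable anti-infective' in Table 2, Annex 2 and the result tables, and add a sentence to Section 9.9 saying that intravenous route cannot be separated from other injection routes.

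The cost is a small programming edit or a label change, ideally before the final report. Under the first option the percentage may come out lower than in results already delivered, and a table note should explain this. Under the second the number stays the same and only its description changes.
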